Super-FIN Trial

Plan for Blinded data interpretation NCT01758796

We, the Blinded Data Interpretation Committee of the SUPER-Fin trial, have reached a consensus on how to carry out the blinded data interpretation (BDI).

The document coined "Minutes for Super-Fin blinded data interpretation" (next page) outlines the execution of the blinded data interpretation for the SUPER-Fin trial.

Statistical analysis will be carried out by the trial statistician without any involvement from members of the Blinded Data Interpretation Committee or other Super-Fin investigators, as outlined below. The central study coordinator will code the trial data (two treatment arms) as 'Group A' and 'Group B' before handing the data over to the statistician. This will help ensure that the statistical analyses will be performed blind to the treatment allocation.

To reduce risk of interpretation bias, blinded results from the ITT analysis (Group A vs. Group B) will be presented to the Blinded Data Interpretation Committee. The Blinded Data Interpretation Committee will then contemplate on two alternative written interpretations, one where group A is the initial non-surgical treatment strategy and one where Group A is the initial surgical strategy. Only after the Blinded Data Interpretation Committee has reached a consensus on the proper interpretation of the findings, the central study coordinator will unblind the treatment group allocation.

Also, as Drs. [name] and [name] were involved in the clinical care of the patients, they will recuse themselves from making any interpretations but are to take part in the blinded data interpretation meeting to answer potential questions regarding the execution of the trial.

Finally, the undersigned (members of the Super-Fin Blinded Data Interpretation Committee) agree that the minutes of the upcoming blinded data interpretation meeting will be emailed to an independent scientist for external review (comments/requests for clarification) before the final manuscript is submitted.

Super-Fin Blinded Data Interpretation Committee

July 18, 2022

[name], PhD (Chair)

[name], PhD (Co-Chair)

[name], Trial statistician

[name] [name]

[name]

[name], PhD

[name]

Minutes for the Blinded Data Interpretation meeting for Manuscript:

Surgery versus Non-surgical Treatment for ER-stress Unstable Weber-B Unimalleolar Fractures (Super-Fin): A Prospective Randomised Non-Inferiority Trial

Super-Fin Blinded Data Interpretation Committee:

The sample size calculation was performed for a two-arm study (surgery vs non-operative treatment). In our previous study assessing surgery for unstable ankle fractures with the same primary outcome,[3] the mean OMAS score was 79.6 (SD 15.5) at the 2-year follow-up. During the design of the present trial, no estimate for minimal clinically relevant change existed for OMAS. In the absence of better evidence, we organized a focus group discussion among experts to define the appropriate estimate for non-inferiority margin. The panel reached a consensus that a 10% difference in 0–100 OMAS scale would not be clinically significant, which was then used to derive our non-inferiority margin (10% equals eight points in the OMAS scale, Cohen's d=0.215, indicating a small effect size). With α =0.05, power 80% (1- β =0.8), a non-inferiority margin of 10% (8 points), and with a dropout rate of 20%, the calculations resulted in 63 patients per group (total n=126).

Statistical analysis

Primary analysis

The trial was primarily designed to ascertain whether initial non-surgical treatment is non-inferior to initial surgery, 2 years after the injury, with the primary outcome, the OMAS. Only the primary analysis, initial non-surgical treatment versus initial surgery, will be used to assess non-inferiority. For the primary time point, non-inferiority of non-surgical treatment to surgery will be claimed if the lower limit of the confidence interval (for differences in means in OMAS) is greater than -8.0 in the primary comparison. According to the CONSORT statement for non-

inferiority and equivalence,[1] secondary outcomes can be managed using either a superiority or an equivalence framework. In our trial, all secondary outcomes will be assessed with a superiority hypothesis, but as the trial was not powered for these comparisons, we will merely consider the data (analyses) as supportive, exploratory, and/or hypothesis generating.

The primary analysis will be performed according to the intention-to-treat principle. In the intention-to-treat analyses, the participants will be included as randomised. The results will be reported following the Consolidated Standards of Reporting Trials (CONSORT) statement. [1,4] We will quantify the treatment effect on an intention to treat basis as the absolute difference between the groups in the OMAS score (primary outcome) with the associated 95% confidence intervals and P values at 24 months after the randomisation (primary time point).

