Short-cycle tertiary education (ISCED 5)		
Bachelor, Master or Doctoral (ISCED 6–8)		
Did not wish to answer or missing		
Place of occurrence (ICD-10) †, No. (%)		
Leisure activity		
Working for income		
Sports activity		
Other		

Figure 1. Trial flowchart (participant numbers to the point of randomization – not beyond, to preserve blinding)

ITT, intention-to-treat; ER, external rotation; OMAS, Olerud-Molander Ankle Outcome Score.

Table 2. Primary outcome at the primary outcome assessment time point (24 months).^a

	Group A		Group B		Difference (95% CI)
	n	Mean \pm SD	n	Mean ± SD	
Primary efficacy outcome					
OMAS (Scale: 0 to 100)	TBA*	?? + ??	TBA*	?? ± ??	?? ± ??

^{*} TBA (to be added, later): To preserve blinding, n-values for Groups A and B will only be added after randomization code is broken.

Our judgment on the efficacy (non-inferiority) will be based on the location of the whole CI in relation to Δ (non-inferiority margin), as outlined by Piaggio et al².

SUPER-Fin / Generic NEW TREATMENT BETTER NEW TREATMENT WORSE Superior A Noninferior В Noninferior Noninferior? D Inconclusive E Inconclusive Inconclusive? G Inferior H Treatment difference for adverse outcome (new treatment minus reference treatment)

As we will not have knowledge of treatment group assignment (whether Group A or Group B is our "new treatment": here, non-surgical treatment), and to preserve our blinding, we have deemed it necessary to take both scenarios under consideration, as follows:

- We will calculate the treatment group difference assuming first that Group A is the "new treatment" and then that Group B is the "new treatment" (Scenario 1 and Scenario 2).
- We will plot the resulting point estimate with error bars (95% Cis) into two separate graphs.
- We will interpret both graphs (Figures 2 and 3).

Figure 2. Scenario 1: Group A minus Group B.

(EXAMPLE GRAPH BELOW, to be replaced by the actual graph of the SUPER-Fin trial data).

[figure not shown]
[figure not shown]

Figure 3. Scenario 2: Group B minus Group A.

(EXAMPLE GRAPH BELOW, to be replaced by the actual graph of the SUPER-Fin trial data).

Initial interpretation:

Based on the location of the whole CI in relation to Δ (non-inferiority margin), our initial interpretation on the non-inferiority of non-surgical treatment (vs. surgery), is as follows:

Scenario 1 (Figure 2)

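### The stated 80% power does not hold: 63 per group with 20% dropout gives about 72% under the plan's 95% confidence interval rule, and 63 does not reproduce at either one-sided 0.025 or 0.05

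*SAP*

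**What the plan says.** The Sample size section of the SAP reports a two-arm calculation. It first cites the group's previous study, where "the mean OMAS score was 79.6 (SD 15.5) at the 2-year follow-up". The inputs to the calculation begin "With α =0.05, power 80% (1- β =0.8"). The margin enters as 8 OMAS points, which the plan equates with 10%. The sentence closes "and with a dropout rate of 20%, the calculations resulted in 63 patients per group (total n=126"). It does not say whether alpha is one-sided or two-sided, and it states no assumed true difference.

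Under Primary analysis, non-inferiority is claimed when the lower confidence limit for the difference in mean OMAS lies above -8.0. That sentence names no confidence level, but the same section reports the treatment effect "with the associated 95% confidence intervals and P values at 24 months after the randomisation (primary time point"). In the efficacy part of the meeting minutes, Table 2 is headed with a 95% interval, and for the two scenarios the plan says "We will plot the resulting point estimate with error bars (95% Cis) into two separate graphs". The committee judges non-inferiority from those graphs. No 90% or one-sided interval appears anywhere in the document.

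**The concern.** Requiring the lower limit of a two-sided 95% interval to exceed -8 is a one-sided test at 2.5%. A sample size computed at one-sided 5% is too small for that rule. Because the sidedness of alpha is not stated, the reader cannot tell which test the 63 was meant to serve, and the obvious check is whether 63 follows from the stated inputs under either reading.

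The trial's chance of a conclusive answer is at stake. Inconclusive is one of the formal conclusions open to the committee. If the real power is well below 80%, that outcome is more likely than the plan implies even when the two strategies are equally good, and the committee and later readers would weigh it against a wrong figure. Unstated sidedness also leaves room for a later dispute over whether a 90% or a 95% interval should decide.

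**Working it through.** **Inputs**, all from the SAP's Sample size and Primary analysis sections: margin 8; SD 15.5 (the only SD given); power 80%; dropout 20%; 63 per group with equal allocation; a 95% interval for the decision. The true difference is taken as 0, which is an assumption because the plan states none.

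**Step 1: try to reproduce 63.** The normal-approximation formula is

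n per group = 2 × SD² × (z₁₋α + z₀.₈₀)² / margin², with 2 × 15.5² / 8² = 480.5 / 64 = 7.508 and z₀.₈₀ = 0.8416.

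- One-sided 0.025: 7.508 × (1.960 + 0.8416)² = 58.9, so 59 analysed (60 by noncentral t).
- One-sided 0.05: 7.508 × (1.645 + 0.8416)² = 46.4, so 47 analysed (48 by noncentral t).

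| One-sided alpha | Analysed per group | Randomised, n / 0.8 | Randomised, n × 1.2 |
|---|---|---|---|
| 0.025 (95% interval) | 59–60 | 74–75 | 71–72 |
| 0.05 (90% interval) | 47–48 | 59–60 | 57–58 |

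The last column covers the common shortcut of multiplying by 1.2 instead of dividing by 0.8. Taking the margin as 7.96 (10% of 79.6) gives 72 to 77 in place of the first row's figures and 57 to 60 in place of the second's. None of these is 63.

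**Step 2: power of the design as stated.** 63 × 0.8 = 50.4, so about 50 are analysed per group. The standard error of the difference is 15.5 × √(2/50) = 3.10, and 8 / 3.10 = 2.581.

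- 95% interval: Φ(2.581 − 1.960) = Φ(0.621) = 73.3%; noncentral t gives 72.4%.
- 90% interval: Φ(2.581 − 1.645) = Φ(0.936) = 82.5%; noncentral t gives 82.1%.

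**Step 3: how much dropout the 95% rule tolerates** (noncentral t).

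| Analysed per group | Loss from 63 | Power, 95% interval |
|---|---|---|
| 50 | about 20% | 72.4% |
| 57 | about 10% | 78.0% |
| 60 | about 5% | 80.1% |
| 63 | none | 82.0% |

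At most 3 of 63 per group can be lost (3/63 = 4.8%) before power falls below 80%. The plan allows for 20%.

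**Step 4: sensitivity to what the plan leaves open**, with 50 analysed per group and the 95% interval. Power is 81% at SD 14, 75% at SD 15, 72% at SD 15.5 and 70% at SD 16. At SD 15.5, if non-surgical treatment is truly worse by 1 point, power is 61%; by 2 points, 48%.

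**The case against.** The strongest reply is that the trial was sized at one-sided 0.05. On that reading 59 to 60 per group suffice, 63 gives 82% power after 20% loss, and recruiting a few more than the minimum is no error. The exact figure can even be recovered if 15.5 was rounded up to 16: the formula then gives 49.5, so 50 analysed, and 50 / 0.8 = 62.5, so 63. This may well be how the number arose. But SD 16 is not in the text, and a one-sided 0.05 test corresponds to a 90% interval while the plan judges by 95%. The explanation identifies the mismatch without removing it. SD 16 at one-sided 0.025 also yields 63 (62.8), but with no dropout allowance, which contradicts the stated 20%.

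A second point is that the sentence listing the inputs names no SD; 15.5 comes from the earlier study reported just before it. That is fair, and the 72% is conditional on it. The section's only other clue, a Cohen's d of 0.215 for the 8-point margin, implies an SD of 8 / 0.215 = 37.2 and would make power far worse. It also disagrees with 8 / 15.5 = 0.516.

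Third, the error is on the cautious side. A 95% interval is stricter than a 90% one, so the risk of a false non-inferiority claim does not rise, and the observed interval will show the precision achieved. This stands, and it limits the seriousness of the point. It does not make the stated power correct.

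Finally, the section reports a past calculation, and writing in one-sided 0.025 could misdescribe how it was done. That is a reason to word the correction as the power under the decision rule, without rewriting the history.

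**Conclusion.** The point holds. With SD 15.5, a true difference of 0, 20% dropout and the 95% interval the plan uses, power against the 8-point margin is about 72%, and the type II error is 28% where the plan implies 20%. The design keeps 80% power only if at least 60 per group are analysed. The 63 does not follow from the stated inputs under either reading of alpha; after the planned dropout it supports 80% only with a 90% interval. Any true disadvantage of non-surgical treatment, or an SD above 15.5, lowers the power further; an SD of about 14 would restore it. The consequence is an overstated chance of a conclusive result, with no increase in the chance of a false non-inferiority claim.

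**What to change.** Replace the power statement in the Sample size section with wording such as: *With 126 randomised and 20% dropout (about 50 analysed per group), SD 15.5, a true difference of 0 and a two-sided 95% confidence interval (one-sided alpha 0.025), power against the 8-point margin is about 72%; it reaches 80% only if at least 60 per group are analysed.* State in the Primary analysis section that the interval compared with -8.0 is the two-sided 95% interval, so that alpha and the decision rule agree. If the sidedness and SD used in the original calculation are on record, report them alongside as the basis of the 63.

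The cost is a sentence or two and a less favourable power figure. No patients are added, and the margin, the analysis and the decision rule stay as they are. The change should be made before the committee sees the results.

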In the only previous study with a similar design to the SUPER-Fin trial, [20] 40% of 40 patients in the non-surgical group reported had "compromised fracture healing": namely, eight fracture displacements and eight with a delayed or non-union. However, only two of these patients required secondary surgery. In the surgery arm, in turn, six patients experienced a post-operative wound infection, but only one required a secondary surgery to revise the wound. In addition, there were four patients treated initially with surgery that required a secondary surgery to remove a symptomatic hardware.

Although data on the exact incidences and long-term effects of downsides/adverse consequences of both treatment strategies is scarce, it seems highly likely that our analysis will be underpowered. Furthermore, both treatment strategies have unique, characteristic adverse consequences that would likely unblind the treatment given for outcome assessors and/or those interpreting the data.

For the above noted reasons, particularly to preserve blinding, we have decided to only assess the incidence of secondary surgery in both groups in our primary efficacy analysis, as we consider this outcome to be most appropriate (blinding-preserving) for comparing the major downsides of the two treatment strategies. However, to be completely transparent and inclusive about the possible effect of adverse consequences on the clinical relevance (interpretation) of our findings, we commit to also considering the rate of non-unions before finalising our interpretation. However, this more comprehensive analysis on the downsides of the two treatments will not change our assessment on efficacy, rather possibly only change the wording of a possible notion on adverse consequences, and accordingly, it will be carried out after we have reached a consensus on efficacy (and unblinded the treatment assignment = broken the randomization code).

The sequence of events to take place in the upcoming "blinded data interpretation meeting" is outlined in the flow chart below:

[figure not shown]

1. Analysis on efficacy (primary, non-inferiority): Is non-surgical treatment non-inferior to surgery?

Table 1. Baseline characteristics.

	Group A	Group B
Characteristic	(n = ??)	(n = ??)
Age at fracture years, mean (SD) [range]		
Patients aged over 50 years, No. (%)		
Gender, No. (%)		
Men		
Women		
Level of education*, No. (%)		
Basic education (ISCED 2)		
Upper secondary education (ISCED 3-4)		

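### The SAP names no model or covariate for the primary OMAS difference; prespecified adjustment for age and sex would be a cheap improvement, not the repair of an error

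*SAP*

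**What the plan says.** The Primary analysis section of the SAP quantifies the treatment effect "as the absolute difference between the groups in the OMAS score (primary outcome"). Its decision rule is worded in terms of a difference in means: the lower confidence limit must exceed -8.0. The interval to be reported is a 95% CI, at 24 months.

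The Table 2 shell has columns only for n, mean ± SD in each coded group, and the difference with its 95% CI. For the committee, the plan is: "We will plot the resulting point estimate with error bars (95% Cis) into two separate graphs". No test, regression model or covariate is named in any of these places.

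The Table 1 shell lists baseline items, starting with "Age at fracture years, mean (SD) [range"], followed by an over-50 category, gender, education and place of occurrence. Under Blinded data interpretation, Table 1 and Table 2 are both put before the committee ahead of its initial interpretation.

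The Sample size section reads: "With α =0.05, power 80% (1- β =0.8), a non-inferiority margin of 10% (8 points"), with SD 15.5 from a previous study and 20% dropout, resulting in 63 patients per group.

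**The concern.** The whole verdict rests on where one 95% interval lies relative to -8. A baseline variable related to 24-month OMAS can narrow that interval if it is included in the model, and age and sex are already planned baseline items. Leaving them out may cost a little precision.

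A second consequence does not depend on precision. The committee sees the baseline table by coded group next to the primary result, and the SAP has no rule for what to do if age or sex happens to be unbalanced. Any allowance would then be a judgement made with the result in view, in a procedure whose purpose is to limit such discretion. A prespecified adjusted estimate removes the question for the covariates it contains.

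**Working it through.** **Inputs.** From the SAP: margin 8, SD 15.5, 63 per group, 20% dropout, and a 95% CI for the decision. Assumptions: a true difference of 0, a two-sided 95% interval (one-sided 0.025), and R-squared, the share of within-group variance in 24-month OMAS explained by age and sex together. The SAP gives no value for R-squared, so a range of 0 to 0.15 is shown.

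**The plan's own figure.** n per group = 2 × SD² × (z_alpha + z_beta)² / margin².
- One-sided 0.025: 2 × 15.5² × (1.960 + 0.842)² / 64 = 58.9, so 59 evaluable; 59/0.8 = 73.75, so 74 per group.
- One-sided 0.05: 2 × 15.5² × (1.645 + 0.842)² / 64 = 46.4, so 47 evaluable; 47/0.8 = 58.75, so 59 per group.

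Neither gives 63. SD rounded to 16 with one-sided 0.05 does: 49.5, so 50 evaluable, and 50/0.8 = 62.5, so 63. The SAP does not say that this was the calculation.

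**Unadjusted power.** Evaluable patients per arm: 63 × 0.8 = 50.4, taken as 50. SE = 15.5 × √(2/50) = 3.10. The critical t on 98 df is 1.984, so the half-width is 1.984 × 3.10 = 6.15. The noncentrality is 8/3.10 = 2.58. Noncentral t power is 72.4% (73.3% by the normal approximation). At one-sided 5% it is 82.1%.

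**Adjusted power.** SE = 15.5 × √(1 - R²) × √(2/50) × √1.021. The factor 1.021 = 97/95 is the expected variance cost of estimating two covariates with 100 patients (exact for normal covariates, approximate here because sex is binary). The t distribution has 96 df, critical value 1.985.

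| Assumed R² | SE | Half-width | Net power |
|---|---|---|---|
| Unadjusted | 3.10 | 6.15 | 72.4% |
| 0 | 3.13 | 6.22 | 71.5% |
| 0.02 | 3.10 | 6.15 | 72.4% |
| 0.05 | 3.05 | 6.06 | 73.7% |
| 0.10 | 2.97 | 5.90 | 76.0% |
| 0.15 | 2.89 | 5.73 | 78.3% |

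Break-even is near R² = 0.02. The worst case loses 72.4 - 71.5 = 0.9 points; the top of the assumed range gains 78.3 - 72.4 = 5.9 points. Without the covariate cost, the R² = 0.15 figure would be about 79.1%, still under 80%.

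**Chance imbalance.** With 50 per arm, the standard error of a baseline difference in age is √(2/50) = 0.2 SD. If age alone explained 5% of the variance (an illustration), its correlation with OMAS would be √0.05 = 0.22, and an imbalance of one standard error would shift the unadjusted difference by 0.22 × 0.2 × 15.5 = 0.7 points. That is small, but it matters if the limit lies close to -8.

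**The case against.** The strongest reply is that nothing here is wrong. A difference in means with a 95% CI is an unbiased estimator in a randomised trial, and the same advice could be given on almost any plan without covariates. This stands, and it is why the point is an improvement only.

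It can also be said that no adjustment is inferred from silence. The SAP never uses the word unadjusted, a model-based effect is also an absolute difference in means, and the protocol, not available to this review, may name a model or strata. This stands in part. The natural reading of the effect definition and the Table 2 shell is a raw difference, but if a model is intended, the SAP still needs to name it.

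The SAP reports no association of age or sex with OMAS. It mentions age only in relation to complications of surgery. This also stands: the gain cannot be claimed as a fact, and below an R-squared of about 0.02 there is a slight loss.

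Finally, the committee does see Table 1 before interpreting, so imbalance is not hidden. But seeing an imbalance is not a rule for handling it.

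**Conclusion.** A low-cost improvement. As written, the SAP describes a simple difference in means and names no model or covariate; that analysis is valid. Prespecifying age and sex would change net power from 72.4% to between 71.5% and 78.3% for R-squared between 0 and 0.15. These figures assume SD 15.5, 50 evaluable per arm, a true difference of 0 and a two-sided 95% interval. The benefit that does not depend on R-squared is a rule, set in advance, for age and sex imbalance.

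Three stronger readings are not supported:
- **That adjustment would bring the trial to its stated 80% power.** It does not anywhere in the assumed range.
- **That the trial is simply underpowered and adjustment is the remedy.** The shortfall depends on reading the 95% CI as two-sided. The sample size text gives α = 0.05 without sidedness, and at one-sided 5% the same inputs give 82.1%. With all 63 per group evaluable, power under the two-sided interval is 82.6% by the normal approximation. The mismatch between alpha, the interval and the sample size is a separate matter, and adjustment does not reconcile it.
- **That the baseline data are known to be complete.** Table 1 is an empty shell, and its education block has a row for missing or declined answers. This is one reason to limit the covariates to age and sex.

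**What to change.** Before the coded data are analysed, add to the Primary analysis section: the primary difference and its 95% CI come from a linear model of 24-month OMAS on coded group, age (continuous) and sex, plus any randomisation stratum the protocol uses; the -8.0 rule is applied to the adjusted difference; the unadjusted difference is reported as a sensitivity analysis. Label the difference column of Table 2 accordingly; the group means and SDs can stay raw.

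Blinding is not affected. The model runs on Group A and Group B, and only the sign of the estimate changes between Scenario 1 and Scenario 2.

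The cost is one sentence and two degrees of freedom, about 1 power point if age and sex turn out to be unrelated to OMAS. If the coded data have already been analysed, the adjusted result should be reported as a sensitivity analysis only. If the sponsor prefers the unadjusted difference, the SAP should say so and state that baseline imbalance will not alter the verdict.
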